The dermatology clinics located in: King Abdullah University Hospital (KAUH), in Princess Basma Hospital, (PBH), King Talal Hospital (KTH), Princess Haya Hospital (PHH) and Prince Rashid Hospital (PRH) and King Hussein Medical Center will be visited for patients interview and data collection. The participants' privacy will be preserved throughout the study and the participants' answers will be kept strictly confidential and never associated with any personal details. This study does not involve any human biological sample. No potential risks will be associated with the participation in the current study. No special safety consideration for isotretinoin drug Except those mentioned above since it approved from 1982. Consent will be obtained from IRB.

Data analysis

After data was collected, the data was entered into Excel worksheets. The responses were coded and entered into SPSS (version 23). Descriptive statistics of categorical and continuous variables were

calculated. For the categorical variables, the frequency and percentage were calculated, while the arithmetic mean and standard deviation were calculated for continuous variables.

The differences in participants' responses were examined using the Chi-square test (between intervention and control groups) and McNamara's test (between baseline and follow up encounters) for categorical dependent variables as appropriate. For continuous dependent variables, One Way Analysis of Variance (ANOVA) test, independent samples t-test, and Wilcoxon test were performed when applicable. Both Kolmogorov-Smirnov Z and Shapiro-Wilk tests were used to test for normality of continuous variables. The statistical significance level was considered at a p-value ≤ 0.05 .

Patients Knowledge and Awareness of Isotretinoin:

The degree of knowledge and awareness of correct practice was calculated as a total score. The patient knowledge section consisted of ten different questions/items, and each item had two answers (yes/no). Items were coded according to the answer; the correct (adequate) answer was coded as one (1), while the wrong (not adequate) answer was coded as zero (0). So, the knowledge score could take the values of 0 (no knowledge) to 10 (perfect knowledge).

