Chi square test was used to measure patients' knowledge regarding isotretinoin use at baseline between intervention and control group. It was also used to measure patients' knowledge regarding isotretinoin use at follow-up between intervention and control group. To measure if there was a significant difference in the correct patient knowledge regarding isotretinoin use, the percentage of the correct response for each question was calculated for both groups in baseline and at follow-up. McNamara's test was performed to test if there was a significant difference in knowledge before the intervention and after the intervention in the intervention group, and at if there was a significant difference in knowledge between baseline and follow-up in the control group. In addition, independent t-test was used to compare the knowledge score differences (knowledge score at follow up – knowledge score at baseline) between the intervention group and the control group. Linear regression was conducted to evaluate the effect of the educational intervention on the difference in knowledge score adjusting to variables that were unbalanced at baseline.

Patients Adherence to the Recommendations

Similarly, adherence to recommendations for appropriate uses provided by clinical pharmacists for correct practice was calculated as a total score for each participant. This section consisted of 10 items for all patients, and each item had answers (yes/no). Items were coded according to the answer; the correct (adherent) answer was coded as one (1), while the wrong (not adherent) answer was coded as

zero (0). The adherence score of patients 'compliance with the recommendations ranged between 0 (least adherent) to 10 (most adherent). Average score was evaluated across the intervention and control groups (using t test).

HADS Scale

HADS questionnaire was analyzed based on the scoring system; which consists of fourteen items; seven items each for the depression and anxiety subscale. The score for each item ranges from 0 to 3, and the HADS score ranged from 0 to 21 for depression and the same applied for anxiety.

Chi square test was used to compare HADS items at baseline between intervention and control group. Besides, it was used to compare HADS items at follow-up between intervention and control group. Independent t-test was used to compare the HADS score differences (between baseline and at follow up) between the intervention group and the control group.

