HADS scores were categorized into three categories based on the abnormality classification; normal (less than eight), borderline abnormal (between eight and eleven) and abnormal (above eleven). Chi square test was used to evaluate the association between HADS score categories and intervention control status at baseline and at follow up.

Patients Adherence to Medication

The percentages (%) of patients' adherence to medication and non-pharmacological adherence were calculated by dividing the number of adherent patients by the total number of patients in both groups. According to the final question, the reasons behind the patient's non-adherence were themed into three distinct groups (forgetfulness, run out, and unavailability of isotretinoin). The frequency (%) of each group was calculated by dividing the number of times each category has occurred over the total number of patients and multiplying by 100. Chi-square test was conducted to evaluate the association between adherence status and patient intervention control status.

Results

1. Baseline Questionnaire Results

A total of 207 patients using isotretinoin in Jordan were randomly recruited to participate in the study. About four patients missed answering the phone in the follow-up phase, so they were excluded from the study. The response rate was 96.7% and 203 patients completed the study as shown in **Figure 1**.

[figure not shown]

Figure 1: Patient recruitment flowchart

1. Demographics of Respondents

The demographics of the participants are summarized in **Table 1**. All baseline demographic and clinical characteristics of the study participants were not statistically different between intervention and control group except for monthly income with P -value=0.032. Most respondents were female ($n=179$, 88.2%) compared to male ($n=24$, 11.8%) in both groups. Most of the patients were in the age group of 18-25 years, and the $mean \pm SD$ of age for the intervention group was 21.68 ± 3.21 and 21.36 ± 2.6 for the control group. Regarding marital status, 96.9% of the participants were single

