while the remaining were married (3.1%) for both study groups. The vast majority of participants have a bachelor's degree in both the intervention (85%) and control groups (86%). Most of the respondents' area of the residence for both groups was from the Irbid (77.8%) and the rest were from other cities (22.2%). Patients in either intervention or control group had a body mass index (BMI) ranged between 18.5 and 24.9 with a percentage of 68.6% and 73%; respectively.

Regarding health insurance, 96.1% of the intervention group and 98% of the control group were insured. For all study participants, the period since starting to use the drug was no more than the first four months. More than half of the participants took a daily dose of 40 mg of isotretinoin in both intervention (58.3%) and control group (57%). The vast majority of the patients in both study groups (99%) had no chronic disease.

Table 4.1: Baseline demographic and clinical characteristics of the study population

Characteristics	Total		Intervention group		Control group		P-value
	n	%	n	%	n	%	
Gender							
female	179	88.20	91	88.30	88	88	0.939
male	24	11.80	12	11.70	12	12	
Age (years)							
18-20	86	42.40	41	39.80	45	45	0.628
21-25	100	49.20	51	49.50	49	49	
26-30	13	6.40	7	6.80	6	6	
31-35	4	1.90	4	3.90	0	0	
Marital status							
single	196	96.90	98	95.10	98	98	0.265
married	7	3.10	5	4.90	2	2	
Educational level							
school	21	10.30	10	9.70	11	11	0.562
college	4	2	2	1.90	2	2	
bachelor	173	85.20	87	85	86	86	
postgraduate studies	5	2.50	4	3.90	1	1	
Profession							
student	146	71.9	74	71.80	72	72	0.525
Unemployed	25	12.3	10	9.70	15	15	
Non-medical profession	16	7.9	10	9.70	6	6	
Medical profession	16	7.9	9	8.70	7	7	
Residential area							
Irbid	158	77.80	80	77.70	78	78	0.949
Alzarqa'a	3	1.50	2	1.90	1	1	
AL Mafraq	13	6.40	7	6.80	6	6	
Amman	19	9.40	9	8.70	10	10	

Jerash	4	2	2	1.90	2	2	
Ajloun	5	2.50	2	1.90	3	3	
Maan	1	0.50	1	1	0	0	
Monthly income							
below 500 JD	28	13.80	17	16.50	11	11	0.032
500-100 JD	111	54.70	47	45.60	64	64	
above100 JD	64	31.50	39	37.90	25	25	
Health insurance							
yes	197	97	99	96.10	98	98	0.428
No	6	3	4	3.90	2	2	
Strength & dose of isotretinoin per a day (mg)							
10	2	1	2	1.90	0	0	0.612
20	55	27.10	26	25.20	29	29	
30	26	12.80	14	13.65	12	12	
40	117	57.60	60	58.30	57	57	
60	3	1.50	1	1	2	2	
Period since starting the current isotretinoin course (months):							
newly diagnosed	42	20.70	22	21.40	20	20	0.603
first month	42	20.70	23	22.30	19	19	

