3 months follow-up, and responses of the patients are shown in **Table 2** and **Table 3**; respectively. Patients' average knowledge score at the first meeting before the education process was 6.5 out of 10. There was no significant difference in overall knowledge score at baseline between the intervention group and the control group with a mean (6.47 for the intervention group vs. 6.57 for the control group).. In contrast, the patient's average knowledge score at follow-up (three months after the education session) was 8.22 out of 10. The results at follow-up showed a significant difference in the knowledge score (P-value<0.001) between the intervention (9.3) and control group (7.1).

The average difference in the overall knowledge score (before and after the education process) was statistically different between the intervention and control group (1.6995 ± 1.589 ; P-value< 0.001). The average difference in overall knowledge score was, 2.835 ± 1.329 for the intervention group and 0.530 ± 0.784 for the control group.

Since the monthly income was significantly different between intervention group and control group at baseline, results from linear regression showed that the difference in overall knowledge score is still significantly different between the intervention and control group after adjustment for income status (Coef. = 2.308446); P-value< 0.001

Table 2: Patients knowledge regarding the use of isotretinoin at baseline

	Intervention group n (%)	Control group n (%)	P-value
knowledge about common side effects			
yes	6 (5.8)	2 (2)	0.28
no	97 (94.2)	98 (98)	
We can use isotretinoin during pregnancy*			
yes	10 (9.7)	10 (10)	0.944
no	93 (90.3)	90 (90)	
We can use the drug without prescription*			
yes	6 (5.8)	5 (5)	0.795
no	97 (94.2)	95 (95)	
No need to have laboratory monitoring during isotretinoin use*			
yes	4 (3.9)	5 (5)	0.745
no	99 (96.1)	95 (95)	
We should drink water to reduce the dryness			
yes	99 (96.1)	98 (98)	0.683
no	4 (3.9)	2 (2)	
We should use sunblock to reduce sensitivity to the sun			
yes	99 (96.1)	99 (99)	0.121
no	4 (3.9)	1 (1)	
It is preferred to take isotretinoin with fatty foods			
yes	70 (68)	74 (74)	0.343

no	33 (32)	26 (26)	
We can donate blood during isotretinoin*			
yes	67 (65)	70 (70)	0.451
no	36 (35)	30 (30)	
Woman can lactate while using isotretinoin*			
yes	72 (69.9)	72 (72)	0.742
no	31 (30.1)	28 (28)	
We can make laser or wax during isotretinoin*			
yes	66 (64.1)	55 (55)	0.188
no	37 (35.9)	45 (45)	

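### The knowledge regression picks its covariate by baseline significance tests, and so adjusts for income while the baseline knowledge score is only subtracted, never modelled as a covariate

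*Combined protocol and SAP*

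**What the plan says.** In the combined protocol and SAP, the Data analysis section on patients' knowledge compares change in the 0 to 10 score (follow-up minus baseline) between arms by an independent t-test. It then adds a linear regression to evaluate the intervention "on the difference in knowledge score adjusting to variables that were unbalanced at baseline". It does not define imbalance or list candidate covariates. The general significance threshold is given earlier in the same section: "The statistical significance level was considered at a p-value ≤ 0.05".

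The results show how the rule was applied. Results 1 (Demographics) reports that the baseline characteristics "were not statistically different between intervention and control group except for monthly income with P -value=0.032". Results 3 (Knowledge) then gives the reason for the adjusted model: "Since the monthly income was significantly different between intervention group and control group at baseline". Income is the only covariate reported, with a coefficient for arm of 2.308446. The mean baseline knowledge scores, 6.47 and 6.57, are reported in the same section, but the score is not a covariate in any model.

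**The concern.** A rule that lets baseline P-values choose covariates leaves the adjusted model to chance. Where allocation is random, a small baseline P-value says nothing about whether a variable predicts the outcome, and the documents give no reason why income should predict knowledge of isotretinoin. The baseline value of the outcome is the natural adjustment variable. The rule could bring it in only if the arms happened to differ on it significantly, and they did not.

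The change score does use baseline, but it forces the slope of follow-up on baseline to be 1. That is a poor choice when one arm ends near the top of a bounded scale: patients who start low and those who start high finish at nearly the same score, so change mostly reflects where they began. At stake are the precision and the defensibility of the adjusted estimate.

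**Working it through.** **1. The selecting test reproduces.** Income counts in the baseline table (Table 4.1) are 17/47/39 v 11/64/25. Expected counts are 14.21/56.32/32.47 v 13.79/54.68/31.53. Pearson chi-square = 1.11 + 3.13 + 2.66 = 6.91 on 2 df, P=0.032, as printed.

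**2. How often the rule selects something by chance.** Table 4.1 has 11 P-values. If the tests are independent and randomisation is sound, P(at least one ≤ 0.05) = 1 − 0.95^11 = 0.43. Independence is an assumption.

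**3. Noise from subtraction, intervention arm.** The follow-up score is the sum of the ten items in Table 3: the correct answers total 959, and 959/103 = 9.31, matching the printed 9.3. Six items are 100% correct and contribute no variance. The SD of each other item is √[p(1−p)]:

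| Item | Correct | SD |
|---|---|---|
| Side effects | 49/103 | 0.499 |
| Water | 100/103 | 0.168 |
| Lactation | 94/103 | 0.282 |
| Laser or wax | 98/103 | 0.215 |

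The SD of a sum cannot exceed the sum of the SDs, 1.165, or 1.17 with the n−1 divisor. If the items were independent it would be about 0.64. The reported SD of change is 1.329.

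Write b for the within-arm slope of follow-up on baseline. Then var(change) = var(follow-up) + var(baseline) × (1 − 2b). Here 1.329² = 1.766 and var(follow-up) is at most 1.17² = 1.369, so var(baseline) × (1 − 2b) is at least about 0.40. Hence b is below 0.5 in this arm, where the change score assumes 1.

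**4. The plan's own effect.** Change difference = 2.835 − 0.530 = 2.305. Pooled variance = (102 × 1.329² + 99 × 0.784²)/201 = 1.199. SE = √[1.199 × (1/103 + 1/100)] = 0.154, 95% CI 2.00 to 2.61, t ≈ 15.0. The income-adjusted coefficient, 2.308, differs by 0.003.

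**5. Effect with baseline knowledge as covariate.** Estimate = change difference + (1 − b) × baseline difference, where b is now the common slope. The baseline difference is −0.10 from the printed means, or −0.08 from the Table 2 item counts (667/103 = 6.476 v 656/100 = 6.56).

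- b = 1: 2.305.
- b = 0.5: 2.255 to 2.263.
- b = 0: 2.205 to 2.221.

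Residual variance = 1.199 − (1 − b)² × var(baseline). The baseline SD is not given. For an assumed SD of 1.0 to 1.5 and b of 0.25 to 1, the SE runs from about 0.08 to 0.154. SD 1.5 with b = 0.25 is left out because it gives a negative residual variance. With SD 1.25 and b = 0.5, for example, residual variance = 1.199 − 0.25 × 1.5625 = 0.808 and SE = 0.126. Even the lowest estimate over the largest SE is 2.205/0.154 = 14.3, so P<0.001 throughout.

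**6. The other baseline P-values.** Uncorrected Pearson chi-square on the printed counts reproduces eight of the 11 values in Table 4.1 (one of them within 0.001). These do not reproduce, the last being from Results 2:

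| Characteristic | Printed P | Recomputed P |
|---|---|---|
| Age group | 0.628 | 0.235 |
| Education | 0.562 | 0.613 |
| BMI | 0.783 | 0.821 |
| Physician informed about side effects (75/103 v 66/100) | 0.327 | 0.292 |

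The BMI counts sum to 102 and 101, but the arms have 103 and 100. None of the four recomputed values is near 0.05.

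**The case against.** The strongest reply is that nothing turns on this. The main knowledge comparison is an unadjusted t-test that the selection rule does not touch, adding income moved the estimate by 0.003, and knowledge is not the outcome that sized the study. That stands, and it limits the point to the soundness and precision of the adjusted estimate.

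It can also be said that the proposed model is itself chosen after the results were seen, that a common baseline slope is doubtful near the ceiling, and that the scale stays bounded whichever model is used. All true. The first calls for plain labelling. The second matters less than it seems: with random allocation, a common-slope model still estimates the average difference, and robust standard errors cover the unequal spread.

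Three stronger readings are tempting but unsupported:

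- **That the faulty P-values led to income being chosen.** Income's own P-value reproduces, and correcting the other four would select nothing further. Some mismatches may not be errors of testing: age was collected as an open field and education in seven levels, so the tests may have used data finer than the printed categories.
- **That baseline depression shows the rule depends on coding.** Splitting HADS depression at above 11 (24 v 12) gives P=0.035, or 0.054 with Yates correction, against 0.108 in three categories. But the plan fixes three categories, and nothing shows HADS was a candidate covariate.
- **That a definite precision gain can be quoted.** A variance ratio of (1 + r)/2 would give a 15% to 35% reduction for r of 0.7 to 0.3, but it requires equal variances at baseline and follow-up. With one arm at the ceiling, that is doubtful.

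**Conclusion.** The point holds as a weakness in the choice of model. The covariate was picked by a rule with about a 43% chance of finding something among 11 independent tests when nothing is wrong, while the outcome's own baseline value was left with a slope fixed at 1. In the intervention arm the documents' figures show that slope to be too high (below 0.5), and the change score noisier than the follow-up score alone. That bound needs no assumed correlation, only that the score is the sum of the ten items, which the printed mean confirms.

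The size of the precision gain cannot be fixed without patient-level data. Under the assumptions above it ranges from none to roughly a halving of the SE (0.154 to about 0.08). A reader might infer that the knowledge finding is in doubt. It is not: the difference stays at about 2.2 to 2.3 points with P<0.001 for any common slope from 0 to 1. The P-values that do not reproduce are a separate reporting matter.

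**What to change.** - Delete the rule that selects covariates by baseline imbalance.
- Fit follow-up knowledge score on arm and baseline knowledge score. Report the adjusted difference with a 95% CI, using robust standard errors because the change SDs differ (1.329 v 0.784).
- Keep the income-adjusted model as a sensitivity analysis. Add months on isotretinoin only if a reason is given for treating it as prognostic.
- State that this model was specified after the data were seen, since the results are already printed.
- Separately, check the P-values for age, education, BMI and being informed by the physician against the source data. Correct the BMI counts, and state which test and which categories were used.

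The cost is one regression on data already held and a few lines of text. The one small downside is the post hoc label.

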After the informed consent (see appendix 1) is taken from each patient who agreed to participate in the study, the participants will be randomly assigned to either an intervention group or a control group. Intervention group will consist of the patients who will receive the educational process (recommendations) about isotretinoin by clinical pharmacists additionally to the usual routine care (education about isotretinoin provided by the physician). Control group will consist of the patients who will receive the usual routine care. Both patients and physicians are unaware of patients' assignment in both groups.

The main task of the clinical pharmacist is to educate patients in intervention group by providing them all information about isotretinoin that can serve the patient during the treatment period, which includes: the degree of the importance of adherence to the drug and the recommendations, the correct method of taking it, the importance, and when, of doing periodic laboratory tests (lipid profile, liver enzyme test, and pregnancy test), and explanation of common side effects, how to avoid and deal with them, and what are the cases in which the drug should be stopped. The detailed information on the recommendation for managing side effects that will be used to educate the patients are provided in Appendix 2.

Patient's adherence to the recommendations, awareness and side effects managements for both groups will be measured through a set of questions adapted from a validated questionnaire after one month and three months of isotretinoin initiation (Appendix 3). The validated questionnaire was adopted from a previous study on patients' knowledge about isotretinoin therapy use in Jordan. The permission to use the questionnaire was obtained from the researcher.

The questionnaire is composed of 41 questions related to: demographics, side effects, physician and clinical pharmacist practice, recommendations and contraindications according to current guidelines, and patients' commitment. In addition, the Hospital Anxiety and Depression Scale (HADS) [22], will be used to evaluate depressive and anxiety symptoms at baseline and during the follow up period in each group. Finally, clinical improvement in acne will be evaluated three months after initiating the treatment from the view of physicians as well as the patients themselves.

Location and safety considerations

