	99 (96.1)	103 (100)	0.045	99 (99)	99 (99)	0.317
It is preferred to take isotretinoin with fatty foods						
	70 (68)	103 (100)	< 0.001	74 (74)	81 (81)	0.0196
We can donate blood during isotretinoin*						
	36 (35)	103 (100)	< 0.001	30 (30)	43 (43)	0.0008
Woman can lactate while using isotretinoin*						
	31 (30.1)	94 (91.3)	< 0.001	28 (28)	40 (40)	0.0027
we can make laser or wax during isotretinoin*						
	37 (35.9)	98 (95.1)	<0.001	45 (45)	60 (60)	0.0011

Frequencies and percentages presented are for correct answers.

At follow-up, patients were asked if they searched for outside sources for information about the drug during their treatment. About 56% of the control group compared to 45% of the intervention group said yes with P-value=0.079.

4. Patient's Adherence to Recommendations About the Proper Use

The patient's adherence to recommendations for the proper use of isotretinoin and the adherence to

specific instructions on managing side effects provided by the physician or clinical pharmacist at follow-up was evaluated. The average recommendation score was 7.601 ± 1.358 for all patients, and it was significantly different between control and intervention group (the mean for intervention group= 8.534 ± 0.905 and control group= 6.64 ± 1.039) with P-value <0.001 . The percentage of participants who were adherent to all recommendations (10 out of 10) was 15.5% for the intervention group compared to 0% for the control group.

The frequency and number for patients who were adherent to the recommendations for the intervention group and control group are summarized in **Table 4.5**. Around 59% of the intervention group compared to 27% of the control group were adherent to drinking plenty of water (more than two liters per day) with P-value <0.001 .

Table 5: Patient's adherence to recommendations about the proper use at follow-up

	Intervention group n (%)	Control group n (%)	P value
I adhere to drink plenty of water during isotretinoin use			
yes	61 (59.2)	27 (27)	< 0.001
no	42 (40.8)	73 (73)	
I adhere to use eye drop during isotretinoin use			
yes	89 (86.4)	69 (69)	0.003
no	14 (13.6)	31 (31)	
I adhere to use lip balm during isotretinoin use			
yes	101 (98.1)	98 (98)	0.90
no	2 (1.9)	2 (2)	
I adhere to use body lotion during isotretinoin use			
yes	48 (46.6)	28 (28)	0.006
no	55 (53.4)	72 (72)	
I adhere to make laboratory monitoring (AST & ALT) during isotretinoin use			
yes	102 (99)	98 (98)	0.618
no	1 (1)	2 (2)	

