- It's good.
- Acceptable
- Weak

26. What is the impact of the side effects on your daily life and your usual activities?

- Big effect
- moderate effect

- Weak effect
- There's no effect.

27. Was the menstrual cycle affected during treatment?

- Yes
- No

- If yes, what is the impact?

- getting late
- getting early
- became heavy
- became light
- its duration became longer
- its duration became shorter

28. Was your treatment affected during the Corona period?

- Big effect
- moderate effect
- Weak effect
- There's no effect.

- If yes, what is the impact?

- Getting the medication
- adherence to medication
- Going for monthly doctor reviews
- adherence to periodic tests

29. Do you think you needed to explain more about the drug in general?

- Yes
- No

30. Do you think you needed to explain more about the drug in terms of the method of use?

- Yes
- No

31. Do you think you need edited more explanations about the side effects of the drug and how to avoid it?

- Yes
- No

32. Do you have any feedback regarding this questionnaire?

- Yes

No

Please answer the following questions regarding adherence to recommendations provided by clinical pharmacist.

	yes	no	I do not know	Not applicable
I adhere to drink plenty of water during isotretinoin use				
I adhere to use eye drop during isotretinoin use				
I adhere to use lip balm during isotretinoin use				
I adhere to use body lotion during isotretinoin use				
I adhere to make laboratory monitoring (AST & ALT) during isotretinoin				
I adhere to make lipid profile test during isotretinoin use				
I adhere to use sunblock when going out during isotretinoin use				
I adhere to take isotretinoin with fatty foods				
I adhere not to donate blood during isotretinoin use				
I adhere not to make laser or wax during isotretinoin use				
I adhere not to breastfeed my child during treatment:				
I adhere to do a monthly pregnancy test				

Please answer the following questions regarding adherence to the medication?

	At all	Rarely	Sometimes	Usually,	Always
Do you forget to take your meds?					
Do you skip medication when you feel better?					
Do you skip taking medications when they're worse after taking medications?					
Have you run out of your medications?					
In general, do you adhere to what your doctor or pharmacist tells you about your lifestyle (food, exercise, smoking...) I don't think					
Can you please tell us what are the most common reasons for not taking your medications?					

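### The recommendation-adherence score gets only an unadjusted follow-up t-test, while the knowledge score also gets a covariate-adjusted model: some precision and consistency are lost, but no bias results

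*Combined protocol and SAP*

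**What the plan says.** **Adherence to recommendations.** Under Data analysis, Patients Adherence to the Recommendations, ten yes/no items are summed to a 0-10 score, and the whole comparison is one sentence: "Average score was evaluated across the intervention and control groups (using t test". No covariate or model is named. The Results match this: section 4 gives arm means, SDs and a p-value, and the item results are in "Table 5: Patient's adherence to recommendations about the proper use at follow-up". No difference with a confidence interval is reported.

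**Knowledge.** The subsection just before it goes further. Knowledge is measured at baseline and follow-up and analysed as a change score by t-test, and a model that allows for imbalances at study entry follows: "Linear regression was conducted to evaluate the effect of the educational intervention on the difference in knowledge score adjusting to variables that were unbalanced at" (quote cut before its last word). Results section 3 reports that model, adjusted for income.

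**When adherence was asked.** The ten items are in Appendix 3, part B (follow-up form), under the line "Please answer the following questions regarding adherence to recommendations provided by clinical pharmacist". Part A (baseline form) has no such block. The Study Protocol schedules the questionnaire "after one month and three months of isotretinoin initiation (Appendix 3").

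**Who was enrolled.** The Results state: "For all study participants, the period since starting to use the drug was no more than the first four months". Table 4.1, in the rows headed "Period since starting the current isotretinoin course (months"), lists 42 of 203 patients as newly diagnosed and the rest in months one to four.

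**The concern.** Adherence is in the study title and is the basis of the sample size (50% v 80%), yet its score gets the simpler of the two analyses. The reason given for adjusting knowledge, a variable out of balance at baseline, applies equally to adherence, because the patients and the imbalance are the same. A reader who sees one outcome adjusted and the other not cannot tell whether the choice was planned.

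Two things are at stake. One is precision: baseline knowledge, months on isotretinoin and income were all recorded, and any of them that predicts adherence would narrow the interval. The other is interpretation: the items were asked only after the intervention, so the report can compare arms but cannot describe change within patients. For example, lip balm use is 98.1% v 98% and each laboratory item is 99% v 98% at follow-up. Nothing shows whether those levels were there before.

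**Working it through.** **1. Reproduce the reported figures.** Results section 4 gives intervention 8.534 (SD 0.905, n = 103) and control 6.64 (SD 1.039, n = 100).

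- Overall mean: (103 × 8.534 + 100 × 6.64)/203 = 7.601, as stated. The combined SD comes to 1.358, also as stated.
- From the Table 5 counts: intervention 879/103 = 8.534, which agrees; control 665/100 = 6.65 against a printed 6.64, which is immaterial here.

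**2. Unadjusted difference.** 8.534 − 6.64 = 1.894. SE = √(0.905²/103 + 1.039²/100) = 0.137. 95% CI = 1.894 ± 1.972 × 0.137 = 1.62 to 2.16. With the pooled SD of 0.973, t = 13.9.

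**3. Precision after adjustment.** SE(adjusted) ≈ SE × √(1 − ρ²), where ρ is the joint within-arm correlation of the covariates with the score. The documents give no value, so ρ is assumed and the difference is held at 1.894.

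| assumed ρ | SE | CI half-width |
|---|---|---|
| 0 | 0.137 | 0.27 |
| 0.1 | 0.136 | 0.27 |
| 0.3 | 0.130 | 0.26 |
| 0.5 | 0.118 | 0.23 |
| 0.7 | 0.098 | 0.19 |

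These values are slightly favourable, because the formula takes the covariates as balanced. Income is not: the chi-square on Table 4.1 is 6.909 (p = 0.032, as stated), and 6.909/203 = 0.034 is the share of the variation in arm that income explains. The variance is therefore inflated by 1/(1 − 0.034) = 1.035 and the SE by about 1.017. At ρ = 0.3 and 0.5 the SEs become about 0.133 and 0.120. Below about ρ = √0.034 = 0.18 nothing is gained.

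**4. How far the estimate could move.**

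- *Income.* The middle band holds 47/103 = 45.6% v 64%. If that band differed from the others by an assumed 0.5 to 2 points, the shift would be 0.09 to 0.37 in either direction. At the extreme, 1.894 − 0.367 = 1.53.
- *Income in the knowledge model.* The unadjusted difference is 2.835 − 0.530 = 2.305 and the adjusted coefficient is 2.308, a move of 0.003. This does not show that income is unrelated to adherence, but it makes the upper end of the range above look unlikely.
- *Baseline knowledge.* The means are 6.47 v 6.57. Even one adherence point per knowledge point would shift the estimate by only 0.10.
- *Already on drug.* 81/103 = 78.6% v 80/100 = 80.0%. If treated and new patients differed by up to 2 points, the shift is at most 0.03.

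**5. Who could have answered at baseline.** 42 + 51 + 57 + 11 = 161, and 161/203 = 79.3%. If first-month patients had only just started, the figure is 161 − 42 = 119, and 119/203 = 58.6%.

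**The case against.** The strongest reply is that nothing is wrong with the test. In a randomised comparison, prior habits are balanced in expectation, and a follow-up-only t-test estimates the arm difference without needing a baseline score. With t = 13.9 and a half-width that goes from 0.27 to 0.26-0.23 at best, the adjusted model is a refinement that alters no conclusion. The assumed correlation of 0.3 to 0.5 would also suit a baseline adherence score better than baseline knowledge, income or months on drug, and nothing in the documents shows that these predict adherence. All of this stands, and it limits the point to precision and consistency.

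A reader might go further and infer that, because most patients were already taking the drug, existing habits cannot be separated from the effect of the session. The documents do not support that. Randomisation identifies the between-arm effect; only within-patient change is out of reach.

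A reader might also pick out the fourth-month row of Table 4.1 (2.9% v 8%). That is 3 v 8 patients in one row of a variable with p = 0.603. Scoring the rows 0 to 4, mean months are 174/103 = 1.69 v 185/100 = 1.85, a gap of 0.16.

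Finally, a baseline block cannot now be collected. It would have been undefined for at least the 42 newly diagnosed patients, and its heading refers to advice that nobody had yet received. This also stands, so that remedy belongs only to a future version.

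**Conclusion.** The point holds as a minor one. The plan adjusts knowledge for a baseline imbalance and leaves adherence, measured on the same patients, unadjusted, without giving a reason. The t-test is valid, so the cost is precision and consistency. With an assumed joint correlation of 0.3 to 0.5, the SE falls from 0.137 to about 0.130-0.118, or about 0.133-0.120 once the income imbalance is counted. With weaker correlation the gain is nil. Even the widest assumed income shift leaves about 1.5 points of a 1.89-point difference, so the direction and significance are not expected to change. The exact adjusted estimate needs patient-level data, which the documents do not contain.

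**What to change.** **Now.** Fit one linear regression of the adherence score on arm, baseline knowledge score, months on isotretinoin and monthly income. Report the adjusted difference with its 95% CI beside the unadjusted 1.89 (1.62 to 2.16). Label it post hoc, because results are already known, and fix the covariate list in writing before fitting so that it is not chosen by its effect on the estimate. Income belongs in it as the one variable reported as unbalanced and the one used in the knowledge model. State that adherence was measured only after the intervention, so within-patient change cannot be reported. The cost is one model on data already held.

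**In a future version.** Name the same adjusted model in advance for both scores. The ten items could also be asked at baseline of patients already on treatment, with the block's heading reworded to suit. An on-drug indicator in the model, with the baseline score set to a constant for new starters, keeps everyone in the analysis. The cost is ten more questions and the risk that asking them prompts better behaviour in both arms.
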